- The informed consent is also presented within the Sonde App before study participants can start their daily study activities (one-time after starting the study). Participants indicate agreement by checking an electronic box. The app also allows participants to review the consent information at any time via the app menus.

5. Follow-up Visits and Travel Expenses

Follow up Visits

There are no formal follow up visits. All patient data will be monitored by the research team to ensure data collection is occurring on a daily basis. If there are any problems with the data, patients will be contacted either via email or telephone to offer help and guidance to the patient if needed.

Patients will also have access to support from the research team via telephone / email if they are having problems with data collection.

Travel Expenses

There will be no compensation or inconvenience payments given for participating in the project.

6. Data Collection

Data Collection Form Completion

- The consent form and other project documents will be stored in the research office in a locked cabinet.
- All participant data will be linked-anonymized and stored on a secure password protected computer.
- All consenting participants will be registered on the study's registration log which will be filed in the study's site file. The registration log will include the participants name, date of birth and study ID.

Interim Analysis

An interim analysis will be conducted at the 1-year point after study start to further inform on how many patients will be needed to complete the study. We will file a protocol amendment with the ethics committee should this number differ significantly from that in the current protocol.

The current estimate of approximately 300 participants rests on assumptions detailed below. These assumptions will be refined at the interim analysis point with the data acquired up to that point, so that the powering can be assessed with greater confidence.

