To determine the ability for the vocal biomarkers to assist in the prediction/ early detection of pulmonary exacerbations in people with cystic fibrosis, it is helpful to consider this performance in terms of sensitivity and specificity of the vocal biomarker data with respect to observed pulmonary exacerbations during the study. Other studies using these biomarkers in respiratory conditions have indicated that approx. 60% sensitivity and 60% specificity could be used as an approximate and somewhat conservative performance level. Sensitivity and specificity calculated from the collected data will be used to calculate odds ratio (2.25 at the given sensitivity and specificity) with a 95% confidence interval and p-value according to customary statistical methods. At the stated assumption around performance, about 60 pulmonary exacerbations would need to be observed and examined to have a p-value at 0.05.

[figure not shown]
From clinical experience in the CF clinic, it can be estimated that following roughly 100 patients with CF over a 12-month period will result in approximately 60 pulmonary exacerbations. Vocal biomarker models are gender dependent, so to assess this level of significance in both genders would require a total of 200 patient participants. Accounting for an as yet unknown degree of missing data and drop-outs from the study would further increase the sample size estimate to somewhere between 200-300.

At the 12-month interim analysis points all figures used in these calculations can be refined from the observations made up to that point.

Data Access / Sharing

- The Sonde health app will collect linked anonymized data. All data will be linked-anonymized and uploaded to Sonde's cloud-based server systems, which meet HIPAA and GDPR requirements. Sonde uses Amazon Web Services (AWS) for all data collection and app deployment. Documentation is available upon request. Collected data is transferred through secure (HTTPS) Protocol and is stored in encrypted form in AWS.
- The home monitoring equipment linked-anonymized data is already being uploaded to a secure NHS approved web-based site to allow researchers within the University of Cambridge to analyse it via Microsoft Azure which implements the transmission integrity and confidentiality control by ensuring that cryptography is implemented through a hybrid model. The following is a high-level list of the symmetric and asymmetric keys used for encrypting and protecting confidentiality of data.

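### The target of about 60 exacerbations per sex is set where the expected p-value just reaches 0.05, which gives only about 54–61% power per sex (1:1 comparators assumed)

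*Protocol*

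**What the plan says.** The derivation is in the Protocol, section 6 (Data Collection), under Interim Analysis.

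- **Assumed performance:** "approx. 60% sensitivity and 60% specificity could be used as an approximate and somewhat conservative performance level".
- **Measure:** an "odds ratio (2.25 at the given sensitivity and specificity) with a 95% confidence interval and p-value".
- **Sizing rule:** "about 60 pulmonary exacerbations would need to be observed and examined to have a p-value at 0.05".
- **Event rate:** "following roughly 100 patients with CF over a 12-month period will result in approximately 60 pulmonary exacerbations".
- **Both sexes:** because the voice models differ by sex, "to assess this level of significance in both genders would require a total of 200 patient participants".

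The section then widens 200 to a range of 200–300. The only reason it gives is an unknown amount of missing data and drop-out. Its headline estimate is approximately 300. It says the assumptions will be refined at the interim analysis "so that the powering can be assessed with greater confidence". No power target is stated in the protocol.

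**The concern.** The derivation puts exactly 60%/60% into a two-by-two table and finds the event count at which that table gives p = 0.05. This fixes the expected result at the edge of significance. Observed tables scatter around the expected one, so roughly half of them fall on the non-significant side even when the assumed performance is true. A count chosen this way therefore has about 50% power, whichever test or comparator ratio was used to find it.

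The section presents the calculation as the basis for powering, and the decision to expand recruitment draws on it. If the voice marker performs exactly as assumed, there is a substantial chance of a non-significant result in a given sex. The marker could then be dropped wrongly, or reported as working in one sex only when the difference is chance.

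**Working it through.** **Inputs.** From the Protocol, section 6, Interim Analysis: sensitivity 0.60, specificity 0.60, p = 0.05, 60 exacerbations (PEX) per 100 patients per 12 months, and 100 patients per sex. Assumed: a two-sided test (suggested by the 95% confidence interval), one non-PEX window per PEX, and independent windows. The comparator count is not in the readable text, and a figure that follows the sizing sentence is missing.

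**1. Reproduce the protocol's figures.**
- Odds ratio = (0.6 × 0.6)/(0.4 × 0.4) = 2.25, as stated.
- Expected table at 60 + 60: 36 positive and 24 negative among PEX windows; 24 positive and 36 negative among non-PEX windows.
- Continuity-corrected chi-square = 120 × (|36×36 − 24×24| − 60)² / 60⁴ = 120 × 660² / 60⁴ = 4.03, p = 0.045. Fisher's exact test gives p = 0.044.
- The smallest count with corrected p ≤ 0.05 is 58 (p = 0.049). This matches "about 60" in the protocol closely.
- Uncorrected Wald test: SE(log OR) = √(2/36 + 2/24) = 0.373; z = ln 2.25 / 0.373 = 0.811/0.373 = 2.18; p = 0.030. Under this test 49 PEX would already reach p = 0.05.
- Participants: 60/0.6 = 100 per sex; 2 × 100 = 200.

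**2. Power at that size.** Both windows' positive counts were enumerated as binomials (0.6 and 0.4), and the probabilities of all significant tables were summed.

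| PEX per sex | Participants, no loss | Power per sex: Fisher/Yates | Power per sex: uncorrected | Both sexes |
|---|---|---|---|---|
| 60 | 200 | 54.0% | 61.2% | 29–37% |
| 90 | 300 | 70.6% | 75.6% | 50–57% |

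The last column squares the per-sex power, treating the sexes as independent: 0.540² = 0.29 and 0.612² = 0.37.

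The Wald approximation at 60 agrees: Φ(2.18 − 1.96) = 0.586. The uncorrected figures exceed 50% more clearly because that test has its p = 0.05 point at 49, not 60.

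**3. Size for 80% power per sex.**
- Wald: (1.96 + 0.842)² × 2 × (1/0.6 + 1/0.4)/0.811² would double-count nothing only at 1:1; it evaluates to 99.5, so about 100 PEX.
- Fisher/Yates, by enumeration: 108 PEX (80.2%).
- Participants: 100/0.6 ≈ 167 and 108/0.6 = 180 per sex, so about 334–360 in total before drop-out. This is above the ceiling of 300.

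**4. One sex-stratified test on the same data.** A Mantel-Haenszel test over two strata of 60 + 60, with the same odds ratio in each, was simulated. Power is 84% with continuity correction and 87% without, on 120 PEX in total.

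**5. Sensitivity to the comparator ratio.** With 60 PEX, power (pooled normal approximation) is 59% at 1:1, 72% at 2:1 and 82% at 5:1. The expected p-value at 60 PEX is then about 0.011–0.018 at 2:1 and 0.004–0.007 at 5:1, and p = 0.05 is reached at 36–44 and 29–35 PEX respectively. A higher ratio therefore raises power, but 60 is then no longer the count the protocol describes.

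**The case against.** **The arithmetic is right and no power is claimed.** This stands. The odds ratio, the p-value and the doubling all reproduce, and no 80% figure appears that could be false. A reader might infer a calculation error; there is none. The fault is the sizing criterion, which is written into the protocol and linked there to powering.

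**The headline is approximately 300, and re-estimation is planned.** It would be wrong to say that the protocol treats 200 enrolled participants as enough. But the excess over 200 is allotted to missing data and drop-outs, and 300 with no loss still gives only 71–76% per sex. The interim would refine performance and event rate. Applying the same p = 0.05 rule to refined inputs would again give about 50% power.

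**The comparator count is unknown.** This stands, and it makes the 54–61% conditional. Daily recordings could supply several non-PEX windows per PEX, but the gain depends on those windows being independent, and the stated 60 would then not be the p = 0.05 point. Either way the sentence needs correcting.

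**Success in both sexes is one reading.** The primary outcomes do not mention sex, and the text asks for significance to be assessed in both sexes without saying the study fails otherwise. The 29–37% should not be quoted as the power of the study. Nor should power be judged at 100 participants: that is the first phase, and no sex-specific significance is claimed there.

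**Conclusion.** The concern holds as a faulty sizing criterion, not as a calculation error. At the assumed 60%/60%, 60 PEX per sex give about 54% (Fisher/Yates) to 61% (uncorrected) power in each sex, and 29–37% if significance in both sexes is required. These figures assume 1:1 comparators, a two-sided 0.05 test, independent windows and 200 evaluable participants split evenly by sex. The general result, about 50% power when the expected p-value lies at the threshold, does not depend on the comparator ratio. Repeated exacerbations or windows within a patient would probably change the effective sample size, and the size of that effect cannot be worked out from the document.

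**What to change.** 1. Replace the sizing sentence with a statement that 60 PEX per sex give about 54–61% power at 60%/60% under the stated comparator ratio, and that about 100–108 per sex would be needed for 80%.
2. State the number of comparator windows per PEX, and recalculate these figures if it is not 1:1.
3. Express the target as PEX with usable voice data, in total and per sex, with participants derived from it.
4. At the interim re-estimation, apply a stated power target in place of the p = 0.05 rule.
5. Keep the sex-specific models, but make the main significance test one sex-stratified (Mantel-Haenszel) odds ratio on all 120 or so PEX (about 84–87% power if the odds ratio is the same in both sexes). Report sex-specific odds ratios with confidence intervals as secondary.

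Cost: the stated power per sex looks less favourable, and sex-specific significance becomes secondary, which is a real change to the analysis and must agree with any SAP. No extra patients are needed. Keeping 80% power separately in each sex would instead take about 334–360 evaluable participants.

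### The interim may re-size the study on the observed sensitivity and specificity, the effect under test, and the protocol states no error control for the final p-value

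*Protocol*

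**What the plan says.** Section 6 (Interim Analysis) places an interim at 1 year to inform how many patients are needed. Of the assumptions behind the estimate of about 300 it says: "These assumptions will be refined at the interim analysis point with the data acquired up to that point". It closes with: "At the 12-month interim analysis points all figures used in these calculations can be refined from the observations made up to that point".

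The first of those assumptions is diagnostic performance: "approx. 60% sensitivity and 60% specificity could be used as an approximate and somewhat conservative performance level". From it come an odds ratio of 2.25 and the sizing statement: "about 60 pulmonary exacerbations would need to be observed and examined to have a p-value at 0.05". The event rate is the second: "following roughly 100 patients with CF over a 12-month period will result in approximately 60 pulmonary exacerbations". Doubling for the two sexes gives 200, and an allowance for missing data and drop-out gives 200-300.

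The final analysis reports the odds ratio "with a 95% confidence interval and p-value according to customary statistical methods".

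Three other statements bear on the size of the problem:

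- Section 1 (Study Design, Rationale) starts with 100 participants and uses an interim at 3 months, not 1 year, to decide whether to expand to as many as 300.
- Section 3 (Sample Size) gives a recruitment range of 100 to 300, so remaining at 100 is allowed.
- Section 6 sends a materially different number through a protocol amendment, so 300 is not a hard cap.

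**The concern.** PEX rate, missing data and drop-out are nuisance quantities. Re-sizing on them leaves the error rate of the final test almost unchanged. Sensitivity and specificity are different, because they are the effect that the odds ratio tests. If the size depends on the effect seen so far, and the pooled data are then tested as if the size had been fixed, the p-value and confidence interval lose their stated error rate.

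The planning target makes this worse. The protocol sizes to the count at which the assumed effect just reaches p = 0.05, and it states no power. Re-applied to an interim estimate, that target calls for no more data when the interim result is already significant, and otherwise for enough data to make it so.

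Precision is a second problem. An interim effect from a few dozen PEX is so uncertain that a chance-high value could wrongly halt expansion and a chance-low value could call for a needlessly large study.

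**Working it through.** **Inputs from the protocol.** Sensitivity and specificity 60%/60%; p = 0.05; 60 PEX per 100 patients per 12 months; range 200-300 (Section 6) or 100-300 (Sections 1 and 3); interim at 3 months or 1 year.

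**Assumptions.** Equal numbers of PEX and control periods; two-sided test, in keeping with the 95% interval; independent observations; normal approximation.

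**1. The plan's own figures.** Odds ratio = (0.6 × 0.6)/(0.4 × 0.4) = 2.25, as stated. For 60% against 40% with equal groups, the count at which the expected result just reaches two-sided p = 0.05 (50% power) is 58 PEX with continuity correction and 49 without. At 60 against 60, Fisher's exact test gives p = 0.044. The stated figure of about 60 therefore reproduces, and it is a target of just reaching p = 0.05.

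**2. Events at each point, at the stated rate.**

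- 100 patients for 12 months: 60 PEX
- 200-300 patients: 120-180 PEX
- 100 patients at 3 months: 60 × 3/12 = 15 PEX
- 30 and 45 PEX stand for a 1-year interim reached before all of the first 100 have completed 12 months

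**3. Re-applying the planning rule.** With n1 PEX and test statistic z1 at the interim, the count at which the observed effect reaches p = 0.05 is

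n = n1 × (1.96/|z1|)²,

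held between a minimum and a cap. With t = n1/n, the chance under no effect that the final unadjusted test rejects, given z1, is

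P(Z > (1.96 − √t·z1)/√(1 − t)) + P(Z < (−1.96 − √t·z1)/√(1 − t)).

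Averaging over z1 ~ N(0, 1) gives the actual two-sided false-positive rate:

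| Interim PEX | Minimum PEX | Cap PEX | False-positive rate |
|---|---|---|---|
| 15 | 120 | 180 | 5.2% |
| 60 | 120 | 180 | 5.8% |
| 15 | 60 | 120 / 180 | 5.6% / 5.8% |
| 30 | 60 | 120 / 180 | 6.2% / 6.6% |
| 45 | 60 | 120 / 180 | 6.8% / 7.4% |
| 60 | 60 | 120 / 180 | 8.7% / 9.4% |
| 60 | 60 | none | 10.9% |

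If the rule aimed at 80% power instead, a 60-PEX interim would give 5.6% (minimum 120, cap 180) or 6.5% (minimum 60, cap 180).

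**4. By sex.** With an even split, each sex has 30 of 60-90 PEX at a 60-PEX interim. These are the same fractions as 60 of 120-180, so the inflation per test is the same.

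**5. Precision of the interim effect.** The standard error of the log odds ratio at 60%/60% is √(2/(0.6n) + 2/(0.4n)). For n = 15 it is 0.745, and the 95% interval around 2.25 is 0.5 to 9.7. For n = 60 it is 0.373, and the interval is 1.1 to 4.7.

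**The case against.** A reader might infer that the plan roughly doubles the false-positive rate. The protocol does not support that as a general statement. It gives no interim significance test, no efficacy stop and no re-sizing formula, and its last sentence on the subject says the figures can be refined, which permits rather than requires. Doubling needs the study to end at the interim count. Yet participants are enrolled for 12 months and nothing cuts off their follow-up at an interim, so an early look would be followed by completion to about 60 PEX. Having all 60 in hand 1 year after study start would need all 100 enrolled at the outset. Within the stated 200-300 range the excess is under one percentage point. All of this stands, and it limits the size of the finding.

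A reader might also infer that the final p-value is definitely unadjusted. That is not established: customary methods do not exclude adjustment, and a statistical analysis plan that is not shown may provide it.

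Finally, this is an exploratory, single-centre observational cohort, and confirmatory safeguards may seem excessive. This argues against banning interim modelling of voice and PEX. It does not remove the point, because the protocol itself says the sizing assumptions will be refined, includes the effect among them, sizes to p = 0.05, and lets the study remain at 100. That goes beyond an omitted detail.

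**Conclusion.** The point holds in limited form. The protocol allows re-sizing on the effect under test, with no rule, no firm cap and no stated error control. If the planning rule is re-applied at the interim, the false-positive rate of a nominal 5% test is:

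- about 5.2-5.8% if 200-300 participants are always recruited;
- about 5.8-7.4% (cap 180 PEX) if an interim at 15-45 PEX is followed by completion to at least 60;
- about 9-11% only if the study can end at a 60-PEX interim (cap 120 PEX to no cap).

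These figures rest on the assumptions listed in the working, above all on equal control periods and on the planning rule being the one used. Which line applies depends partly on whether the interim is at 3 months or at 1 year, so Sections 1 and 6 must be reconciled. Whatever the error rate, an effect estimated from 15-60 PEX is too imprecise to set the sample size.

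**What to change.** In Section 6 (Interim Analysis), replace the reference to all figures with a list: PEX rate, missing recordings, drop-out, sex split and within-participant correlation. Keep 60%/60% as the planning value.

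If the sponsor wants the observed effect to drive the size, pre-specify the re-sizing rule with its minimum and cap, together with a weighted combination test or group-sequential boundary and matching confidence intervals.

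In either case, state one interim time consistently in Sections 1 and 6.

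The cost is wording. Under the first option the planning effect is not updated mid-study; under the second the final test is slightly less efficient. Exploratory voice-PEX modelling during the study can continue, provided it does not set the sample size of an unadjusted test.
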